7.7.5 Safety analyses

The safety analyses will be performed using the safety set.

7.7.5.1 Growth and development

Growth and development data collected during the study will be summarized descriptively at each relevant time point. These data consist of height, height velocity (difference of height over 1 year), weight, weight velocity (difference of weight over 1 year) reported as standard deviation score (SDS, also called z-score), the age at the larche (Tanner stage 2 for breast development) and menarche for girls, the age of adrenarche for boys as well as the Tanner stage assessment.

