5.2 Overview of Philadelphia positive acute lymphoblastic leukemia (Ph+ ALL)

Acute lymphoblastic leukemia (ALL) is the most common malignancy in the pediatric population (approximately 80% of childhood leukemias and 25% of all pediatric cancers), with an annual incidence rate of 1-4 new cases per 100,000, with a peak incidence at ages 2-5 years (Pui et al. 2008, Stanulla and Schrappe, 2009). Philadelphia positive acute lymphoblastic leukemia (Ph+ ALL) is characterized by the presence of the Philadelphia chromosome, a reciprocal translocation between chromosomes 9 and 22 (t(9;22)(q34;q11)) resulting in the fusion of the breakpoint cluster region (bcr) gene on chromosome 22 with c-abl gene sequences translocated from chromosome 9 and the expression of the BCR-ABL protein. Ph+ ALL accounts for up to 5% of pediatric ALL (Faderl et al. 2002).

Factors affecting the risk of ALL relapse include age, white blood cell (WBC) counts at diagnosis, presence and type of genetic abnormalities, and response to initial induction therapy. With regard to clinical factors, a poorer outcome is associated with children <1 year and >9 years of age and those with an increasing leukocyte count (Pui et al. 2006, Pui et al. 2008). Pediatric patients with B-lineage ALL are categorized as low risk, standard risk, high risk or very high risk (VHR) (Pui 2001a, Pui et al. 2001b). Pediatric Ph+ ALL is a subtype of VHR ALL, characterized by an older age (median 9-10 years vs. approximately 4-years for all pediatric ALL patients) and higher WBC counts at diagnosis. The presence of the Ph+ chromosome renders a patient very high risk ALL with a high risk of relapse and poor prognosis.

The treatment of ALL is not homogenous. Patients with high risk disease are at higher risk of relapse and receive more intensive chemotherapy than low risk patients. There is no standard chemotherapy regimen in ALL. Treatment of newly diagnosed ALL patients typically consists of several treatment phases, i.e. induction, consolidation, and maintenance. Prior to the development of imatinib, Ph+ ALL patients were treated with intensive chemotherapy followed by hematopoietic stem cell transplant (HSCT), ideally with a matched related donor, as this was shown to result in improved event-free survival (EFS) compared to either HSCT with other donors or chemotherapy alone (Arico et al. 2000).

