7.1.4 Definition of the end of study

The end of study is defined as the point when a minimum of 5 years of observational followup data are available for each enrolled patient, or such available data until early discontinuation (Section 7.2.5), as measured from the date of start of imatinib treatment.

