7.2.2 Inclusion Criteria

Patients eligible for inclusion in this registry have to meet **all** of the following criteria:

- 1. Male or female, pediatric patients aged greater than 1 year (≥365 days) and less than 18 years old (<17 years, 365 days) at diagnosis.
- 2. Documented, newly diagnosed Philadelphia Chromosome-positive (Ph+) acute lymphoblastic leukemia (ALL).
 - Recorded presence of t(9;22)(q34;q11) is required e.g. determined via institutional cytogenetics or FISH and/ or of the presence of BCR-ABL fusion transcript identified by RT-PCR or FISH.
- 3. Enrolled into this registry within 6 months of diagnosis or enrolled in a clinical trial within 6 months of diagnosis, although no earlier than Jan-2012.
- 4. Previously treated or currently on treatment with any chemotherapy regimen + imatinib (of an HA-approved formulation or HA-approved Glivec[®] generic) ± HSCT.
- 5. Written informed consent obtained prior to any information being entered into the registry (parent / legal guardian consent, where applicable).
 - Assent from a patient enrolled as a minor by parent / legal guardian consent **must** be obtained wherever possible. Obvious child dissent **must** be respected.
 - A patient enrolled as a minor by parent / legal guardian consent **must** be re-consented as an adult upon reaching the legal age of maturity during the course of the registry (legal age of maturity defined by local regulations).
 - Patients fulfilling the inclusion criteria, but who have died prior to registry opening and without the opportunity to give consent, may still be eligible for inclusion, subject to local requirements regarding the consent process.

The registry participating physician must assess whether there are any third-party agreements limiting the clinical trial patient's data collection as part of the non-interventional study given that no identification of proprietary treatment information will take place.

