7.4.2.10 Tanner stage and development assessments

Tanner staging will be evaluated as a measure of pubertal status (Tanner 1-5). Data corresponding to the age of menarche for girls and the age of adrenarche for boys will be captured, if available.

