7.7 Data analysis

All analyses will be performed by a Novartis representative and/or designee.

All data summaries and analyses will have descriptive purposes only with no formal inferential testing.

Due to the observational nature of this registry, it is expected that some specific endpoints may not be available at all time points and for the entire population. Unless otherwise specified in the Reporting Analysis Plan, the analyses will be performed on available data.

Patient efficacy, safety and tolerability outcomes of patients treated with chemotherapy + imatinib will be summarized overall, by HSCT (yes/no) and by risk group (good-risk/induction-responder) / (poor-risk/induction non-responder).

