7.7.4.4 Methods of analysis

The efficacy endpoints will be summarized descriptively for the FAS.

Time to event endpoints (OS, EFS, transplant, engraftment) will be described using Kaplan Meier plots and associated statistics such as estimated survival rates by time points and medians along with 95% confidence intervals.

Event rates will be provided with 95% confidence intervals using Pearson-Clopper method.

On top of these analyses, analyses with a different definition of endpoint or on different subgroups will be performed:

- Analyses of OS and EFS will be performed taking into account the occurrence of transplantation procedure (by censoring at time of transplant for example). This is to avoid that prolongation in time to event after transplantation is taken as an Imatinib success.
- OS and EFS will be performed on the following subgroups:
 - subgroups based on age (with age categories selected to allow pubertal vs prepubertal differentiation),
 - subgroups based on peripheral lymphoblast count,
 - subgroups based on enrollment into approved clinical studies
 - subgroups based on type of transplant donor
- Time to transplant will be analyzed and presented according to type of transplant donor (autologous, allogeneic, syngeneic, other).

In addition, an analysis will be performed to evaluate the influence of prognostic factors (age, leukocyte count and early response, type of donor etc.) on efficacy outcome: these could include analyses of the impact of prognostic factors either on the odds of non-response to induction therapy by using logistic regression modeling or on time to event variables using cox regression modeling.

The association between MRD with other endpoints such as OS and EFS will be explored.

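### Summarising only the available ages at thelarche, menarche and adrenarche understates any pubertal delay: children not yet there drop out, and those past the milestone before imatinib are mixed in

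*Protocol*

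**What the plan says.** Protocol section 7.7.5.1 states that "Growth and development data collected during the study will be summarized descriptively at each relevant time point". The variables it then lists include age at thelarche (defined there as breast Tanner stage 2) and "menarche for girls, the age of adrenarche for boys as well as the Tanner stage assessment". It gives no rule for a child who has not reached a milestone, or for one who reached it before treatment.

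Section 7.4.2.10 says of the collection: "Data corresponding to the age of menarche for girls and the age of adrenarche for boys will be captured, if available". Section 7.7 sets the default: "Unless otherwise specified in the Reporting Analysis Plan, the analyses will be performed on available data". Section 7.7.4.4, which covers efficacy, says "Time to event endpoints (OS, EFS, transplant, engraftment) will be described using Kaplan Meier plots". No pubertal age is in that list.

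**The concern.** Age at a pubertal milestone is a time to event on the age scale, and in this registry it will often be censored. Section 7.2.2 admits "pediatric patients aged greater than 1 year (≥365 days) and less than 18 years old", section 5.2 gives a median age at diagnosis of 9-10 years for this disease, and section 7.1.4 ends the study once "a minimum of 5 years of observational followup data are available for each enrolled patient". A child diagnosed at 4 and followed for the minimum period is last seen at about 4 + 5 = 9 years, usually before these milestones.

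Two things follow if only recorded ages are summarised. First, late-maturing children are the ones most likely to have no age, and a real delay enlarges that group. Second, children already past the milestone when imatinib started supply ages that cannot show a treatment effect, and their share of the recorded ages grows as late children drop out. Both errors make the result look more normal than it is. Growth and development is a listed objective (Table 6-1) of a post-authorisation safety study, so an error towards reassurance is the less welcome direction.

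**Working it through.** The protocol gives no figure for this endpoint, so there is nothing to reproduce. The size was examined by simulation.

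**Inputs from the protocol.** Age at diagnosis 1 to under 18 (7.2.2), median 9-10 (5.2); follow-up of at least 5 years (7.1.4); at least 50 patients (7.5).

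**Assumptions not in the protocol (menarche case).** Normal age at menarche 12.7 years, SD 1.2; age at diagnosis mean 9.5, SD 4.2; follow-up 5-8 years; a delay of 0, 1 or 2 years added only in girls not yet menarchal at diagnosis. About 22% of girls are past menarche by then.

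| True delay (years) | 0 | 1 | 2 |
|---|---|---|---|
| Girls with a recorded age | 78% | 71% | 62% |
| True median, all girls | 12.70 | 13.52 | 14.43 |
| Mean of recorded ages | 12.57 | 13.22 | 13.78 |

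**Step 1, true shift in the median.** 13.52 − 12.70 = 0.82 years; 14.43 − 12.70 = 1.73 years.

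**Step 2, visible shift against the same summary without delay.** 13.22 − 12.57 = 0.65; 13.78 − 12.57 = 1.21. Lost: 0.82 − 0.65 = 0.17 and 1.73 − 1.21 = 0.52.

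**Step 3, visible shift against the assumed norm of 12.70.** This is the likely comparison, because the registry has no contemporary control (7.9). 13.22 − 12.70 = 0.52; 13.78 − 12.70 = 1.08. Lost: 0.82 − 0.52 = 0.30 and 1.73 − 1.08 = 0.65.

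**Step 4, mean against mean.** Steps 1 to 3 set an observed mean against a true median. With 22% unaffected, the true mean moves by 0.78 × 1 = 0.78 and 0.78 × 2 = 1.56. The losses are then 0.78 − 0.65 = 0.13 to 0.78 − 0.52 = 0.26, and 1.56 − 1.21 = 0.35 to 1.56 − 1.08 = 0.48. The direction is the same and the size somewhat smaller.

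**Step 5, where the loss comes from.** Among girls not yet menarchal at diagnosis, the mean of recorded ages moves by 0.97 and 1.94 years, nearly the full delay. Most of the dilution therefore comes from mixing in girls past the milestone before treatment. That near-recovery relies on diagnosis ages being spread widely around puberty.

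**Step 6, other assumptions.** Milestone mean 11 or 12.5 years, SD 1.1; diagnosis ages uniform over 1-18 or normal around 9.5 with SD 4.5; follow-up 5 or 7 years.
- No recorded age at 5 years: 21-38% without delay, 36-50% with a 2-year delay.
- Mean among all who reached the milestone: moves 0.36-0.66 years for a 1-year delay and 0.58-1.23 for 2 years.
- Mean among those who reached it after diagnosis: 0.97-1.01 and 1.95-2.00.
- Kaplan-Meier median with entry at diagnosis: 1.10-1.20 and 2.15-2.30. The slight excess reflects how the delay was simulated: no child can have the event during the first year or two after entry, yet is counted at risk.
- Kaplan-Meier of all children, including those past the milestone: 0.45-0.75 and 0.80-1.60. Censoring alone is not enough; the entry rule matters.

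**Step 7, precision.** Assuming half of 50 patients are girls (25), the standard error of the mean recorded age is about 0.3-0.4 years, as large as the 0.30-year loss for a 1-year delay.

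**The case against.** The strongest reply is that the protocol does not fix a faulty method. Section 7.7.5.1 names neither a mean nor a restriction to children who reached the milestone. Section 7.7.4.4 also calls the efficacy summaries descriptive and then applies Kaplan-Meier, so the word does not exclude it. That list sits under efficacy and omits duration of first complete remission, also a time to event, so absence from it proves little. Section 7.7 leaves room for the analysis plan, which is not shown. All of this stands and lowers the weight of the point. What remains is that, on the protocol's own defaults, a child without a recorded age has nothing to contribute.

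A reader might infer that the plan hides pubertal delay. It does not: the mean of recorded ages still moves, and Tanner stage, collected from baseline to study completion (Table 7-1), is summarised with children still at stage 1 included. A reader might also infer that detecting delayed puberty is a stated aim. Table 6-1 says only that growth and development will be assessed, naming height, weight and Tanner staging as examples.

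A last objection also stands: a blank age may mean not reached or not recorded, since ages are captured only where available and section 7.4.1 imposes no visit schedule. Censoring every blank as not reached could push ages upward.

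**Conclusion.** The point holds as an understatement of limited size. Taken on its defaults, the planned age summary omits children not yet at the milestone and mixes in those past it before imatinib. Under the menarche assumptions, about 0.2-0.3 of a 0.8-year shift in the median is lost for a 1-year delay, and about 0.5-0.65 of 1.7 years for a 2-year delay. These sizes depend on the assumed milestone ages, the spread of diagnosis ages, the length of follow-up and the pattern of delay, none of which the protocol supplies in full. The direction, towards younger ages, was the same in every setting tried for the summary of all recorded ages. Severity is minor: this is part of a secondary objective in about 50 patients, sampling error is as large as the smaller bias, no hypothesis is tested, and the primary EFS analysis is untouched.

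**What to change.** In section 7.7.5.1, or in the analysis plan with a reference from it:
- Analyse age at thelarche, menarche and adrenarche by sex with Kaplan-Meier on the age scale. The main analysis covers children documented as not yet at the milestone at imatinib start, entering at that age.
- Censor at the last assessment that documents the milestone as not reached. Where only Tanner visits bracket thelarche, use an interval-censored estimate.
- Report the numbers already past the milestone at imatinib start, reaching it afterwards, censored, and of unknown status. Do not treat a blank age as not reached.
- Keep the Tanner stage summary as planned.

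The cost is analysis wording and a few outputs. No extra assessment is imposed, but the analysis depends on milestone status being documented. Tanner stage does not give menarche status, so some girls may fall into the unknown group. With about 25 children per sex (an even split of 50), and fewer once those already past the milestone are set aside, estimates will be imprecise and a median may not be reached.

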7.7.5.2 Adverse events (AEs)

The incidence of - adverse events (new or worsening from baseline) will be summarized by system organ class and or preferred term, severity (based on CTCAE grades), type of adverse event, relation to study treatment.

Deaths reportable as SAEs and non-fatal serious adverse events will be listed by patient and tabulated by type of adverse event.

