7.3.1.8 Safety

• Adverse events (including serious adverse events) from start of imatinib (Glivec[®]) treatment.

Solicited safety information including serious adverse event reports, if any, will be handled through the Chief Medical Office and Patient Safety (CMO&PS) drug safety surveillance process (Section 9).

An adverse event is defined as the appearance of (or worsening of any pre-existing) undesirable sign(s), symptom(s), or medical condition(s) that occur after a patient starts imatinib treatment.

All adverse events are to be collected and recorded for this registry regardless of relatedness (suspected or non-suspected). In order to comply with the 2012 EMA legislation on adverse event reporting in non-interventional trials, adverse events that are suspected to be related to

imatinib (Glivec[®]) are required to be reported to competent health authorities. Adverse events identified as part of this registry will be included in the annual study progress reports to the EMA.

In the context of this registry, adverse events will be collected in the clinical database (eCRF) from the date of start of imatinib (Glivec[®]) treatment. For further details on AE collection and reporting, including laboratory abnormalities, refer to Section 9. Accurate reporting of SAEs occurring during this period will be verified in accordance with the Site Monitoring Plan (Section 7.8.3).

• Information on all AEs is included in the individual patient eCRFs which must be updated in the registry database on a periodic basis, but not later than one month of new information becoming available.

For the duration of the registry, SAE reporting should continue via normal procedures, through the local Novartis CMO&PS office, as detailed in Section 9. Reporting and follow-up is independent of participation in the registry, although reconciliation will occur.

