9.1 Adverse event definitions and reporting

An adverse event (AE) is defined as the appearance of (or worsening of any pre-existing) undesirable sign(s), symptom(s), or medical condition(s) in a patient administered imatinib (Glivec[®]) that does not necessarily have a causal relationship with the treatment.

An AE can therefore be any unfavorable and unintended sign (including an abnormal laboratory finding), symptom, or disease temporally associated with the use of imatinib (Glivec[®]), whether or not related to the medicinal product(s).

Abnormal laboratory values or test results constitute adverse events only if they induce clinical signs or symptoms, are considered clinically significant, require therapy or require changes in medication(s) dose.

Adverse events that begin or worsen during imatinib (Glivec[®]) administration should be recorded in the Adverse Events CRF. Conditions that were already present at the time of diagnosis and until the first dose of imatinib (Glivec[®]) should be recorded in the Medical History page of the patient's CRF. Adverse event monitoring should be continued for at least 30 days (or 5 half-lives, whichever is longer) following the last dose of treatment. Adverse events (including lab abnormalities that constitute AEs) should be described using a diagnosis whenever possible, rather than individual underlying signs and symptoms. When a clear diagnosis cannot be identified, each sign or symptom should be reported as a separate Adverse Event.

Adverse events will be assessed according to the Common Terminology Criteria for Adverse Events (CTCAE).

The occurrence of adverse events should be sought by non-directive questioning of the patient at each visit during the study. Adverse events also may be detected when they are volunteered by the patient during or between visits or through physical examination, laboratory test, or other assessments. As far as possible, all adverse events should be recorded on the Adverse Events case report/case record form (CRF) with the following information:

- 1. the severity grade (CTCAE Grade 1-4)
- 2. its relationship to the drug(s) of interest (suspected/not suspected)
- 3. its duration (start and end dates or if continuing at final exam)
- 4. action taken with respect to imatinib (Glivec[®]) treatment during registry period (no action taken, dose adjusted/ temporarily interrupted, permanently discontinued, unknown, not applicable)

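### Adverse event incidence is split by HSCT yes/no per patient but not divided at the transplant date, so the overall and HSCT-yes columns pool events before and after transplant

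*Protocol*

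**What the plan says.** Section 7.3.1.8 states that "adverse events will be collected in the clinical database (eCRF) from the date of start of imatinib". Section 9.1 sets a minimum end: "Adverse event monitoring should be continued for at least 30 days (or 5 half-lives, whichever is longer) following the last dose of treatment". Table 7-1 also marks adverse events at the post-treatment follow-up visits and at study completion, and it records transplantation on treatment, at end of treatment and during post-treatment follow-up. Adverse events that start after a transplant can therefore enter the database.

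On analysis, Section 7.7.5.2 says that "adverse events (new or worsening from baseline) will be summarized by system organ class and or preferred term", and continues with "severity (based on CTCAE grades), type of adverse event, relation to study treatment". Section 7.7 sets the strata for efficacy and safety alike: outcomes "will be summarized overall, by HSCT (yes/no) and by risk group". Neither section divides a child's follow-up at transplant.

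For OS and EFS, Section 7.7.4.4 adds analyses that allow for transplant ("by censoring at time of transplant for example") and gives the reason: "This is to avoid that prolongation in time to event after transplantation is taken as an Imatinib success". No similar step is stated for safety.

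**The concern.** Safety is a main secondary objective (Table 6-1) of a post-authorization safety study requested because the safety database was small. A natural question is what adverse events children experience on chemotherapy + imatinib before any transplant, and what is added afterwards. The planned columns cannot answer it for transplanted children.

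HSCT yes/no classes each child by something that happens later. The HSCT-yes column adds together events before, around and after transplant. The HSCT-no column loses all pre-transplant experience of the transplanted children, and it includes children who died or left the registry before a transplant could take place. The overall column depends on how many children happened to be transplanted.

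Section 7.9 names concurrent chemotherapy as a source of mixed adverse events but does not mention transplant.

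**Working it through.** The protocol states no adverse event rate, transplant share or sample-size calculation, so there is no figure to reproduce. The check has two parts.

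**What each planned output can separate**

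- Overall incidence (Sections 7.7 and 7.7.5.2): pools time before and after transplant.
- HSCT-yes: pools both periods in the same children.
- HSCT-no: contains no transplant time, but is a subset defined by a later event.
- Relation to study treatment (Section 7.7.5.2): Section 9.1 records it as suspected or not suspected for the drug of interest. It helps with imatinib, but it is not a judgement between the chemotherapy + imatinib combination and transplant.
- Acute and chronic graft versus host disease and engraftment failure (Section 7.7.4.3): reported separately, but these are only some of the complications of transplant.

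None gives adverse event incidence before transplant for the whole Safety Set.

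**Illustration of size (the three inputs p, h and q are assumptions)**

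Let p be the incidence of an event on chemotherapy + imatinib without transplant, h the share transplanted, and q the added probability of the event after transplant, taken as independent of the earlier period.

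- HSCT-no = p
- HSCT-yes = 1 − (1 − p)(1 − q)
- Overall = p + h(1 − p)q

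With p = 0.20, h = 0.5 and q = 0.5:

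- HSCT-no = 20%
- HSCT-yes = 1 − 0.8 × 0.5 = 60%
- Overall = 0.20 + 0.5 × 0.8 × 0.5 = 40%

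Keeping p = 0.20, the overall figure runs from 0.20 + 0.3 × 0.8 × 0.2 = 24.8% (h = 0.3, q = 0.2) to 0.20 + 0.7 × 0.8 × 0.8 = 64.8% (h = 0.7, q = 0.8).

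Falling back on the HSCT-no column costs precision. At the planned minimum of 50 patients, Clopper-Pearson 95% intervals for a 20% incidence are:

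| Patients | Events | 95% interval |
|---|---|---|
| 50 (whole set) | 10 | 10.0% to 33.7% |
| 35 (HSCT-no, h = 0.3) | 7 | 8.4% to 36.9% |
| 25 (HSCT-no, h = 0.5) | 5 | 6.8% to 40.7% |
| 15 (HSCT-no, h = 0.7) | 3 | 4.3% to 48.1% |

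The whole-set row is idealised. Stopping at transplant shortens time at risk, so a crude pre-transplant percentage would fall below p.

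**The case against.** The strongest reply is that table layout belongs in the analysis plan, which is not shown and may already contain a split by period. Section 7.7.5.2 does not forbid one. That has weight. But the protocol itself fixes the safety strata, and it deals with transplant for OS and EFS in its own text, so the one-sided handling can be read there.

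A reader might go further and infer that transplant toxicity is being counted as toxicity of imatinib. The protocol does not support that. Section 9.1 defines an adverse event without requiring a causal link, so an all-causality incidence attributes nothing. Relation to study treatment is a planned dimension of the summary. The HSCT-no column carries no transplant toxicity. The registry population is, by its title, treated with or without HSCT, so an overall rate that includes transplant time is a legitimate description of it.

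A reader might also conclude that the pre-transplant figure should replace the main safety result. That would ask more of safety than of efficacy: primary EFS and OS are not cut at transplant (Sections 7.7.4.1 and 7.7.4.2), and the transplant analysis is an addition. Nor does the argument reach the growth summaries in Section 7.7.5.1, which describe status at each time point and do not accumulate events.

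Finally, how fully adverse events are captured after transplant is uncertain. Required monitoring is tied to the last dose, and the protocol does not say whether imatinib continues through or after transplant. If capture is low, there is less pooling than in the illustration.

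**Conclusion.** The point holds in limited form. The overall and HSCT-yes columns pool events before and after transplant. The ever-transplanted split cannot show the safety of chemotherapy + imatinib in children who go on to transplant. Relation to study treatment and the separate graft versus host disease rates help only in part. The supplementary transplant analysis given to OS and EFS has no safety counterpart.

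The size cannot be taken from the protocol. The illustration shows the direction, and that the effect could be material, but it depends wholly on the assumed p, h and q and on independence between periods. The planned summaries are not wrong as descriptions; they are incomplete. The change is worth making, but it does not invalidate the plan.

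**What to change.** Keep the overall and HSCT yes/no adverse event summaries and label them as including post-transplant time. Add to Section 7.7.5.2 a supplementary tabulation by period, with patient-years and exposure-adjusted rates:

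- **(a)** From the first imatinib dose to the day before first transplant, or all follow-up if never transplanted, for the whole Safety Set.
- **(b)** From the transplant date onward, for transplanted patients only.

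Assign each event to a period by its start date. Count as patient-years only the time during which adverse events were collected, since Section 9.1 and Table 7-1 leave the end of collection open.

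The transplant date (Section 7.4.2.6) and the adverse event start date (Section 9.1) are already recorded, so no new data are needed. The cost is a few lines of text and one extra set of tables. Transplanted children contribute less time at risk to period (a), so its results should be read per patient-year and not as crude percentages.
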